While on the mother's chest, the newborn's well-being will be initially evaluated by the nurse and respiratory therapist per hospital cesarean section protocol. APGAR scores will be obtained, and the pulse oximeter will be applied to the newborn's right hand. Suctioning needed at that time will be performed using a bulb or mechanical suction. The nurse will remain near the patient's head, as long as needed to ensure maternal and neonatal well-being. Should the mother develop complications that prevent her from being able to comfortably hold the newborn, such as nausea/vomiting, fatigue, or drowsiness from medications, the nurse will be available to help with the newborn. As long as the patient remains stable, the newborn will be laid on mother's chest in a way that allows suckling. The newborn vitamin K administration and erythromycin ointment can be applied per hospital protocol, either while she is holding the newborn or after she is in recovery. The newborn will be weighed following surgery, while the mother is transferred to her bed, unless she requests it be done earlier.

Method 2: Traditional cesarean

Standard preoperative preparation will be performed in the patient's room, including surgical site hair clipping, chlorhexidine wash (at ASMC only), IV placement, completion of pre-procedure operating room checklist, and administration of prophylactic antibiotics, antiemetics (at ASMC only), and fluids. The patient will then be taken to the operating room. The pulse oximeter will be placed on the mother's finger, and electrocardiogram leads will be placed in the usual fashion on the chest. Regional spinal anesthesia will be administered in normal fashion. The mother will lie down on the bed, and fetal heart tracing will be monitored until adequate block is obtained to confirm fetal well-being.

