- If offered to view the birth of her baby, was the drape dropped? (0=No; 1=Yes)*
- Was mom/other support person offered baby right away? (0=No; 1=Yes)*
- Physician Name
- Did family bond occur in the OR? (0=No; 1=Yes)*
- Time from birth to initiation of family bond (minutes)*
- Person who initiated family bond (0=Mother; 1=Father; 2=Other Support Person)*
- Family bond interrupted in the OR (0=No; 1=Yes)*
- Reason family bond interrupted in the OR*
- If the family bond DID NOT occur, why not?*

-
- Surgical site infection associated with this surgery (0=No; 1=Yes)
 - Time to skin-to-skin contact & all other related skin-to-skin variables identified
 - Breastfeeding status flowsheet data (3=Unknown; 2=No; 1=Yes)

Neonatal Variables of Interest

- Birth weight
- 1-min APGAR
- 5-min APGAR
- Documented neonatal infection (0=No, 1=Yes)
- Newborn heart rate at 10 minutes*
- Newborn respiratory rate at 10 minutes*
- Newborn temperature at 10 minutes*
- Time taken for newborn to reach oxygen saturation >90%*

Assessment of patient satisfaction will be conducted following delivery. Questions from an 11-item questionnaire will be asked of the patient by the study coordinator, [name], or one of the resident physicians or the nurses/charge nurses at ASMC and study coordinator, [name], or one of the nurses or charge nurses at ABMC. Please see the questionnaire displayed in a separate document.

Please note, that while we aim to obtain the OR worksheet and patient satisfaction survey from all patients enrolled in the study, there may be circumstances in which one or the other were not completed. If a patient has either the OR worksheet or the patient satisfaction survey completed, we will not exclude them from the study/analyses, but it will be adjusted for.

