For each outcome of interest, we will also develop a mixed regression model to examine the fixed main and interaction effects of Method and Preference. All models will be structured with appropriate response distributions, likely including the lognormal (normal distribution with natural log-transformed response) for continuous responses (e.g., time, weight, vitals), multinomial for survey questions of satisfaction, and binomial for 2-category outcomes (e.g., breastfeeding). Following back-transformation or exponentiation of parameter estimates, model results will be interpreted, respectively, as the percentage difference between groups, ratio of odds of a lower value, and ratio of odds of an outcome occurring. Unobserved outcome heterogeneity will be captured by the delivering physician nested within hospital, each combination of which will define a separate random variable and model intercept.

IX. POTENTIAL RISKS AND BENEFITS

Risks associated with Method 1 (family-centered cesarean delivery) include unforeseen patient and/or family discomfort with viewing the surgical field. Patients will be made aware of the potential risk of such discomfort prior to consenting to participating in the study. Notably, risks of this nature are a normal component of any cesarean delivery. Therefore, we will discuss the risk of viewing discomfort with all patients regardless of study participation. An additional risk associated with participating in either method could be loss of confidentiality due to obtaining limited protected health information. However, to minimize risk, all data will be stored on a password protected computer.

A potential benefit of our study is that we may be able gather level-1 evidence to support local, regional, and possibly broader use of a novel method of cesarean delivery, currently being explored nationally and internationally. We hypothesize that there will be improved maternal satisfaction using the family-centered method. We also hypothesize that neonatal morbidity will not be increased and benefits may include earlier skin-skin contact and greater likelihood of breastfeeding.

X. REFERENCES

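### Newborn vitals have no planned out-of-range outcome, and the percentage difference likely to be reported for temperature depends on the charted unit

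*Combined protocol and SAP*

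**What the plan says.** Section VII, under the neonatal variables, lists three vitals, each with one time point: "Newborn heart rate at 10 minutes", "Newborn respiratory rate at 10 minutes" and "Newborn temperature at 10 minutes". No temperature unit is given. The other neonatal variables are birth weight, the 1- and 5-minute APGAR scores, documented infection and the time to reach oxygen saturation above 90%.

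Section VIII plans a mixed regression model for each outcome. Among the response distributions it names as likely is the lognormal, a "normal distribution with natural log-transformed response) for continuous responses (e.g., time, weight, vitals"), and for that family it says that "model results will be interpreted, respectively, as the percentage difference between groups". Two-category outcomes get a binomial model. The same section also promises descriptive summaries of outcomes within and across the four Method by Preference groups: frequencies, means with 95% confidence intervals, and medians with interquartile ranges.

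Neither section defines a normal range, an abnormal-value category or a margin for any vital. The tertiary objective (Section II) is to find out whether maternal and neonatal outcomes differ by method. Sections I and IX both hypothesize no added neonatal harm.

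**The concern.** There are two separate problems.

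The first is the effect measure for temperature. A percentage difference needs a scale with a true zero. Heart rate and respiratory rate have one; temperature in °C or °F does not. The same physical difference therefore gives two different percentages, and neither has a clinical meaning. A result well under one percent invites the reader to dismiss it, whatever it amounts to in degrees.

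The second is what a comparison of means, or of log means, can show. For all three vitals, values that are too low and values that are too high both matter. If one method produced more of each, the averages could agree while more newborns were outside the normal range. The trial hypothesizes that morbidity is not increased, yet no planned vitals outcome counts abnormal newborns. Similar averages could then be read as reassurance that they do not give.

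**Working it through.** **Group size.** The documents give no sample size or power for vitals, so I take the trial's own total. Section V states 508, from a difference of 0.5 with SD 2 (or 15 minutes with SD 60 minutes), alpha 0.05 and power 0.80. With two-sided alpha (assumed): n per group = 2 × (1.960 + 0.842)² × (2/0.5)² = 251.2, so 252, or 504 in total. The t-based version gives 253 per group (506), which rounds up to 508 for four equal cells. The stated figure reproduces. Half of 508 is 254 per method.

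**Temperature unit.** Assumed means 36.9 and 36.7 °C.
- Celsius: 0.2/36.9 = 0.54%.
- Fahrenheit: 36.9 × 1.8 + 32 = 98.42 and 36.7 × 1.8 + 32 = 98.06; 0.36/98.42 = 0.37%.
- The Celsius percentage is about 1.48 times the Fahrenheit one for the same difference.

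With an assumed SD of 0.4 °C and a purely illustrative limit of 36.5 °C, the share below the limit moves from Φ(−1.0) = 16% to Φ(−0.5) = 31%.

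**Does the log scale lose the shift?** No. Under the same assumptions, z = 0.2 / (0.4 × √(2/254)) = 0.2/0.0355 = 5.6. For a smaller shift of 0.1 °C, z = 2.8 and power = Φ(2.82 − 1.96) = 0.80. A simulation of that case (4,000 runs) gave 81.2% power on the log scale in either unit and 81.1% untransformed.

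**Balanced rise at both ends.** Assume equal log means, a log-SD of 0.10 in controls, and a range that leaves 5% of controls outside (±1.96 SD). If the spread in the other arm is k times wider, its out-of-range share is 2Φ(−1.96/k). Rejection rates are from 4,000 simulated trials with 254 per arm.

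| k | Out of range | Log-mean test rejects | Proportion test rejects |
|---|---|---|---|
| 1.25 | 11.7% | 5.5% | 79% |
| 1.4 | 16.1% | 4.9% | 99% |
| 1.5 | 19.1% | 5.4% | 99.95% |

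The log-mean test stays at its false-positive rate throughout.

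**What proportions cost in precision.** For a rise from 5% to 10% with 254 per arm, the pooled proportion is 0.075, with standard error √(2 × 0.075 × 0.925/254) = 0.0234 under no difference and √((0.0475 + 0.09)/254) = 0.0233 under the alternative. Power = Φ((0.05 − 1.96 × 0.0234)/0.0233) = 57%. The same formula gives 81% for 5% versus 12% and 97% for 5% versus 15%.

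For the 0.1 °C shift above, the shares below 36.5 °C are Φ(−1.0) = 15.9% and Φ(−0.75) = 22.7%. The proportion test then has about 49% power, against about 80% for the mean.

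**The case against.** The case against is substantial, and most of it stands.

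- **The model is provisional.** Section VIII calls the lognormal a likely choice among appropriate distributions, so an untransformed temperature model is already allowed. That is true, but lognormal is the only model named for vitals, and nothing directs temperature elsewhere.
- **Descriptive summaries already help.** Group means and medians in recorded units would put temperature in degrees in front of the reader, and interquartile ranges could hint at wider spread. This stands in part. The modelled effect would still be a percentage, and quartiles are a poor guide to the extreme ends.
- **Masking needs balance.** The excesses must roughly cancel, and the documents give no mechanism by which either method would do this. That is right. It is a possibility that the plan cannot exclude, not a predicted effect.
- **For a plain shift, the mean is the better detector.** The 0.1 °C case shows it, which is why the proportions should not replace the means.

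Three stronger readings are tempting, and the documents do not support them. A reader might infer that the log scale would hide cooling. It would not: the 0.2 °C example gives z of about 5.6. A reader might infer that the vitals carry most of the safety evidence. They are 3 of 8 listed neonatal variables, and the tertiary objective also covers maternal outcomes. Finally, a reader might infer that the 10-minute reading misses the harm because the exposure goes on longer. Under Method 1, "The newborn will be weighed following surgery, while the mother is transferred to her bed, unless she requests it be done earlier", and Method 2 newborns may stay in the warmer until surgery ends, so thermal conditions can differ after the reading. But the documents do not show that later cooling occurs, or that a later temperature is charted at comparable times in both arms.

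**Conclusion.** The point holds in a limited form. A percentage difference is the wrong effect measure for temperature: its size differs by a factor of about 1.48 between units, while the test result barely changes. For all three vitals, the plan lacks an outcome that could show a rise in abnormal values in both directions, and its comparison of location has no power against a balanced one.

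The temperatures, SDs, limit, out-of-range rates and widening factors are assumptions. The unit effect is plain arithmetic, and the blindness to balanced tails follows from the type of model; neither depends on those particular values. The power figures assume 254 complete records per arm and ignore clustering by physician. The 10-minute vitals are marked as OR Worksheet items, and Section VII accepts that some worksheets will be missing, so actual power would probably be lower.

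The primary and secondary results are unaffected. This is a modest gap in the tertiary safety evidence, worth closing because it costs almost nothing.

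**What to change.** In Section VIII:

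1. Take newborn temperature out of the lognormal, percentage-difference group. State its unit and report the difference between methods in degrees with a 95% confidence interval.
2. For each 10-minute vital, keep the mean comparison and add the proportion outside a newborn normal range. The investigators should fix one range for both hospitals before the analysis. It should not be derived from trial data, since Section VII says that interim analyses have already been done.
3. Analyse those proportions with the binomial model already planned, and show low and high counts separately by arm. At an assumed 5%, a cell of 127 yields only about 6 events (127 × 0.05), so state in advance what will be reported if the model with interaction and physician intercepts cannot be fitted.

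The cost is a few lines of plan text. No new data, patients or procedures are needed, and the primary analysis does not change. The downside is lower precision for proportions (57% power for 5% versus 10%), so they supplement the means.

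A later temperature abstracted from EPIC is optional, and useful only if one is routinely charted at comparable times in both arms.

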The secondary objective of this study is to determine if skin-to-skin contact (i.e., family bond initiation) occurs earlier and in-hospital breastfeeding initiation is more likely with the family-centered cesarean delivery method than traditional cesarean delivery method.

Tertiary Objective

The tertiary objective of this study is to determine if differences in maternal and neonatal outcomes exist between cesarean delivery methods (family-centered versus traditional cesarean).

III. STUDY DESIGN

Subject Enrollment

[figure not shown]
Women undergoing a scheduled cesarean delivery at ≥ 38 weeks of gestation who present at Aurora Sinai Medical Center and Aurora BayCare Medical Center and have their babies delivered by obstetrics and gynecology physicians during June 1, 2016 through May 31, 2019 will be enrolled in this study. Patients who meet the study criteria will be recruited via obstetrics and gynecology physicians on the day of their scheduled cesarean section. Patients who agree to participate in this study will be formally consented. The study will be described to the patient using the following script, containing objective language so as to minimize bias or influence when the patient is later asked to identify her preference of the 2 cesarean delivery methods. Note that Method 1 below describes the family-centered delivery method, while Method 2 describes the traditional delivery method.

“We are conducting a patient satisfaction study on two methods of cesarean section. Both of these methods are used throughout the United States, and neither has been proven to be better than the other. Method 1 involves lowering part of the surgical drape exposing a transparent window through which you can watch the birth of your baby; the baby will be placed on your chest immediately after the delivery. Cleaning and evaluation of your baby will be done by a nurse who is standing next to you at the head of the bed. Method 2 involves keeping the surgical drape up throughout the entire surgery so that the birthing process will not be visible, and your baby will be taken to the warmer to be evaluated and cleaned after birth but is available to be laid on your chest at any point upon request.”

Randomization to Method

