Eligible patients will be formally consented on the day of their scheduled cesarean sections by the research coordinator, resident physician(s), charge nurse or nurse. Following enrollment, each patient will be asked to state which method of cesarean delivery she would prefer, if given the option to choose. Preference represents a potential factor influencing patient satisfaction that will be later incorporated into the statistical analysis, based on a 2 x 2 factorial (Method x Preference) design. Documentation of preference at this time (versus following random assignment to cesarean delivery method) is important for minimizing the bias or influence of the random assignment upon the patient’s declared preference.

The patient will be randomized to 1 of the 2 delivery methods by the research coordinator, resident physician(s), charge nurse or nurse, who will present the patient with a sealed envelope. The envelope will contain a slip of paper identifying the patient’s random assignment to either the family-centered cesarean delivery method (Method 1) or the traditional delivery method (Method 2). Fifty percent of all envelopes preassembled for patients will contain paper slips stating “Family-centered”, while the remaining 50% will contain slips stating “Traditional,” allowing for a 1:1 allocation of delivery methods.

Assessment of patient satisfaction following delivery

The primary objective of this study is to compare levels of patient satisfaction with the birthing experience between the two cesarean delivery methods. To assess patient satisfaction, each patient will be verbally surveyed by the study coordinator using an 11-item questionnaire. Similar to the questionnaire used by Armbrust and his colleagues⁶, items on our questionnaire will relate specifically to the mother's birthing experience and answers available per item will be in the form of a modified Likert scale, ranging from 1, the lowest level of agreement or degree of satisfaction, to 5, the highest level of agreement or degree of satisfaction. The survey questions will be asked before discharge (approximately within 48 hours after the delivery), to allow sufficient opportunity for the mother and newborn to bond before discharge.

IV. STUDY POPULATION

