In our study, a factorial design with 2 design variables (Cesarean Delivery Method [Gentle, Traditional] and Preference of Method [Gentle, Traditional]) will be used. A sample size of 508 total patients (127 patients in each of the 4 Method x Preference combinations) has been determined necessary to detect a 0.5-point difference in mean satisfaction scores (on a 5-point scale) and a 15-minute difference in time-to-initiation of family bond between the 2 groups of each design variable, given 2-factor generalized linear modeling with normally-distributed (or log-transformed) responses, standard deviation of 2 points (for satisfaction score) and 1-hour (for family bond initiation), alpha of 0.05, and power of 0.80. Moreover, to detect a 15% difference in probability of breastfeeding prior to discharge between the 2 groups of each design variable using logistic regression, a sample size of 432 total patients (108 patients in each of the 4 Method x Preference combinations) would be necessary. To detect clinically-relevant differences for all outcomes (responses) of interest in the Primary and Secondary Objectives, we will target 508 total patients.

VI. DESCRIPTION OF DELIVERY METHODS

Method 1: Family-centered cesarean

Standard preoperative preparation will be performed in the patient's room, including surgical site hair clipping, chlorhexidine wash (at ASMC only), IV placement, completion of pre-procedure operating room checklist, and administration of prophylactic antibiotics, antiemetics (at ASMC only), and fluids. The patient will then be taken to the operating room. The pulse oximeter will be placed on the mother, and the electrocardiogram leads will be placed away from anterior chest wall or via an EKG back-patch to allow space for newborn and mom skin contact. Regional spinal anesthesia will be administered in normal fashion. The mother will lie down on the bed and, once sufficient anesthesia block is obtained, her gown will be removed and a blanket will be provided for her to cover her chest, allowing for easier skin-to-skin contact after delivery. Prior to the lowering of the drape, the mother's head will be elevated. Fetal heart tracing will be monitored until adequate block is obtained to confirm fetal well-being.

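### Weight is named as a response to be modelled on delivery method, but the only weights collected are settled before randomisation and delivery method cannot change them

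*Combined protocol and SAP*

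**What the plan says.** Section VIII (Statistical Plan) sets one model structure for everything: "For each outcome of interest, we will also develop a mixed regression model to examine the fixed main and interaction effects of Method and Preference". It then matches distributions to types of outcome and proposes the lognormal "for continuous responses (e.g., time, weight, vitals"). Estimates are back-transformed and read as a percentage difference between groups.

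The tertiary objective in Section II is to "determine if differences in maternal and neonatal outcomes exist between cesarean delivery methods". Section VII does not say which collected variables are outcomes under that objective. It contains two weights: the mother's weight in pounds, listed with height and BMI, and birth weight, which is the first item in the neonatal list.

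On timing, Section III (Randomization to Method) says: "Eligible patients will be formally consented on the day of their scheduled cesarean sections". The woman then states her preference, and the envelope is opened after that.

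Section VI puts the weighing of the newborn at different points. Under Method 1 it follows surgery, while the mother is being moved to her bed, unless she asks for it sooner. Under Method 2 it is done at the warmer, after the initial evaluation and along with the measurements and bath.

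**The concern.** A response in a treatment model should be something that treatment could change. Neither weight is. The two methods differ in lead placement, gown, head position, drape, and where the newborn is received and evaluated. None of these acts on the mother's weight as recorded for BMI, or on the weight of a fetus delivered the same day. Section IV treats fetal weight as something that can be estimated before enrolment, since it excludes women on that estimate.

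The Method term for weight therefore cannot inform the tertiary objective. If it came out significant, the plan as worded would report it as a percentage difference between delivery methods, in a trial that says in Section IX that it hopes to supply level-1 evidence. Birth weight has a better use: it is already collected, Method cannot alter it, and it could serve as an adjustment covariate in the models for newborn measures.

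**Working it through.** **1. The plan's own figure.** Section V gives no power for weight, so the figure to reproduce is the total N.

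- Inputs (Section V): "detect a 0.5-point difference in mean satisfaction scores (on a 5-point scale) and a 15-minute difference in time-to-initiation of family bond"; "standard deviation of 2 points (for satisfaction score) and 1-hour (for family bond initiation), alpha of 0.05, and power of 0.80". Two-sided alpha is assumed.
- SD divided by difference is 2/0.5 = 4 for satisfaction and 60/15 = 4 for family bond.
- Per group: n = 2 × (1.960 + 0.842)² × 4² = 2 × 7.849 × 16 = 251.2, so 252, or 504 in total.
- The t-based total is 504.3. Spread over four equal cells, 504.3/4 = 126.1, which rounds up to 127, and 4 × 127 = 508. The stated N is reproduced.
- With even cells each Method group has 2 × 127 = 254 women, and the power is 0.804.

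**2. Rejection probability for weight when Method has no effect.**

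- Method main effect: 0.05.
- Method or interaction, if independent: 1 − (1 − 0.05)² = 1 − 0.9025 = 0.0975.
- Simulation check: 4,000 trials of 508 women, log weight regressed on Method, Preference and their interaction. The assumptions were mean 3,400 g, SD 450 g, an even Preference split, a 50 g Preference difference, no Method effect, and no physician intercept. Method was rejected in 4.7% of trials, the interaction in 5.3%, and either one in 9.8%.

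**3. How large a chance difference would be reported.**

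- Critical difference in SD units: 1.960 × √(2/254) = 0.174.
- The documents give no SD for birth weight. For an assumed SD of 400 to 550 g, an observed difference of about 70 to 96 g would be significant (0.174 × 400 = 70; 0.174 × 550 = 96).

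**4. Could the difference in weighing time matter?**

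- The documents give no size for it. Assume a shift g of 5 to 10 g between arms.
- Rejection probability = Φ(g/SE − 1.96) + Φ(−g/SE − 1.96), with SE = SD × √(2/254).
- SD 400 g: SE = 35.5 g, giving 5.2% at 5 g and 5.9% at 10 g.
- SD 550 g: SE = 48.8 g, giving 5.1% at 5 g and 5.5% at 10 g.
- On these assumptions the artefact adds less than one percentage point.

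**The case against.** **The word sits in a list of examples.** The sentence is about choosing distributions, not about naming outcomes, and no objective mentions weight. Inclusion in the Section VII lists does not make a variable an outcome, since the maternal list also holds the record number and height. This is fair, and it is one reason the point is small. It does not remove it: the sentence calls weight a response, the same paragraph applies the Method and Preference model to every outcome, and nothing limits weight to description. Nor does it matter which weight was meant, because Method can change neither.

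**Five percent is the error of any single null test.** This is also true. What sets weight apart is that the test can have no true positive, so the error buys nothing.

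**Stronger readings that the documents do not support.**

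- A reader might count all three model terms and quote 1 − 0.95³ = 14.3%. That treats Preference as null. Preference is the woman's own stated choice, so a real association with maternal or birth weight is possible.
- A reader might say that any Method difference in recorded weight must be a chance finding. Weighing at different points in the two arms could also produce one. That would be measurement bias, though still not an effect of Method on weight. The contrast is also not clean, since a Method 1 mother may ask for earlier weighing.
- A reader might infer that the plan leaves birth weight out of its check of group comparability. Section VIII gives no variable list for that check, so the omission cannot be shown.

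**Moving birth weight to the descriptive table would not by itself end the testing.** Section VIII also plans significance tests on patient characteristics across the four Method by Preference cells. This objection stands in full, and the fix has to deal with it.

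**Conclusion.** The point holds. As worded, Section VIII makes weight a response to Method, and that test cannot say anything about the tertiary objective. A significant Method term has a 5% probability by chance, and Method or the interaction 9.75% if independent. Under the assumed weighing-time shift of 5 to 10 g, the Method figure rises to at most 5.9%.

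The conclusion rests on three things: that weight means one of the two weights in Section VII; that recorded maternal weight is a pre-delivery value, as its place beside height and BMI suggests; and that the methods differ only as Section VI describes.

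The impact is minor. The documents do not support any inference that the primary comparison of satisfaction, the secondary outcomes or the sample size is compromised.

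**What to change.** In Section VIII:

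- Delete weight from the examples of continuous responses.
- State that birth weight will be summarised by randomised Method as a descriptive characteristic, without a significance test. Without those last words it would fall under the tests that Section VIII plans for patient characteristics.
- Prespecify birth weight as a covariate in the models for newborn temperature, other newborn vitals and Apgar.

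The cost is a one-line edit and one extra term in those neonatal models. No new data are needed and N is unchanged. The gain in precision from the covariate cannot be calculated, because the documents give no correlation between birth weight and the neonatal measures. The case for it is that the value is already collected and Method cannot alter it.

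### Satisfaction is sized as one test of mean scores, but the listed analysis models the survey questions, of which there are 11, and the supplied text gives no deciding variable and no multiplicity rule

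*Combined protocol and SAP*

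**What the plan says.** **Objective.** Section II makes satisfaction under the two delivery methods the primary comparison. It does not say which score or item represents satisfaction.

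**Instrument.** Under Section III (Assessment of patient satisfaction following delivery), each patient is "verbally surveyed by the study coordinator using an 11-item questionnaire". Each item is answered on a scale "ranging from 1, the lowest level of agreement or degree of satisfaction, to 5, the highest level of agreement or degree of satisfaction". Section VII places the questionnaire itself in a separate document.

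**Sizing.** Section V sizes the trial to "detect a 0.5-point difference in mean satisfaction scores (on a 5-point scale"), with a "standard deviation of 2 points (for satisfaction score"), a normal or log-transformed response, alpha 0.05 and power 0.80. The total is 508, that is "127 patients in each of the 4 Method x Preference combinations".

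**Analysis.** Section VIII plans a mixed model for each outcome with Method, Preference and their interaction, and random intercepts for physician within hospital. Its list of response distributions is worded as likely rather than fixed. For satisfaction the entry is "multinomial for survey questions of satisfaction", to be read as an odds ratio for giving a lower answer.

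**Interim looks.** Section VII says that interim analyses are performed during the study and that they led to a revision of the satisfaction survey, dated 2/16/2018.

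**The concern.** The sample size describes one number per patient and one test. The analysis section describes models of survey questions, in the plural, and the survey has 11 of them. Nothing in the supplied text connects the two: it names no total, average or designated overall item, and no rule for reading 11 results together.

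No single result therefore decides the primary objective. A report that one nominally significant item shows higher satisfaction with family-centered cesarean would not breach the plan, and neither would a report based on an average. Section IX hopes for level-1 evidence, and a primary claim of that kind needs a known false-positive rate. The 0.05 in Section V supplies one only for an analysis that Section VIII does not list.

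**Working it through.** **1. Reproduce 508.** Inputs from Section V: difference 0.5, SD 2, alpha 0.05, power 0.80. Sidedness is not stated.

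- Per arm, two-sided, normal approximation: n = 2 × [(1.960 + 0.842) × 2 / 0.5]² = 251.2, rounded up to 252, so 504 in total.
- The t-based version gives 253 per arm, 506 in total. Rounded up to four equal cells this is 508.
- Power with 254 per arm: standard error 2 × √(2/254) = 0.177; 0.5/0.177 = 2.82; Φ(2.82 − 1.96) = 0.80. The two-factor F test gives 0.803.
- A one-sided test would need 396, which does not match.

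So 508 is correct for one two-sided test of one mean score. It contains no allowance for 11 tests.

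**2. False-positive chance over 11 items (illustration).** Assume no Method effect on any item, each item tested at two-sided 0.05, and any one significant item counted as success. The plan neither states nor excludes this rule.

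- Independent items: 1 − 0.95¹¹ = 0.431.
- Independent items, only the direction favoring family-centered (0.025 each): 1 − 0.975¹¹ = 0.243.
- Correlated items: test statistics taken as normal with a common correlation r, integrated numerically. The documents give no correlation, so a range is shown.

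| Assumed r | Either direction | Favoring family-centered |
|---|---|---|
| 0 | 43% | 24% |
| 0.3 | 37% | 19% |
| 0.5 | 30% | 15% |
| 0.7 | 22% | 11% |
| 0.8 | 18% | 9% |
| 0.9 | 13% | 7% |
| One test | 5% | 2.5% |

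Eleven questions about one birth are unlikely to be independent, so the first row is a ceiling, not an estimate.

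**3. Is power at risk?**

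- The largest population SD possible on a 1-to-5 scale has half the answers at each end: √(0.25 × 4²) = 2. Section V already uses this maximum. For one test of 0.5 points with 254 per arm, power is 0.80 at SD 2, 0.98 at an assumed SD of 1.4 and above 0.99 at an assumed SD of 1.0.
- For one item in a proportional-odds model, the odds ratio detectable with 80% power is exp √{6 × (1.960 + 0.842)² / [254 × (1 − Σp³)]}. Three answer distributions are assumed. Answers spread evenly (1 − Σp³ = 0.960) give 1.55. Proportions 0.02, 0.03, 0.10, 0.25, 0.60 (0.767) give 1.63. Proportions 0.01, 0.02, 0.05, 0.12, 0.80 (0.486) give 1.85.
- With the log odds ratio split evenly around each distribution, these are mean shifts of about 0.35, 0.21 and 0.17 points, all below the planned 0.5.

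Clustering by physician is ignored throughout.

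**The case against.** **The mismatch of models does no harm.** A reader might infer that sizing on means and analysing with a multinomial or ordinal model is itself an error. It is not. Step 3 shows that an ordinal test of one item can detect shifts smaller than 0.5 points, and the model list is tentative. This objection stands. What remains is the number of tests and the missing deciding variable.

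**The trial is not underpowered.** A reader might infer a shortfall, because Bonferroni over 11 items at SD 2 would need 868 patients and leaves power 0.49 at 508. But SD 2 is the scale maximum; at an assumed SD of 1.5 the same correction has power 0.82 at 508. The plan also does not call for Bonferroni. No shortfall is shown.

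**Method is already the primary comparison.** A reader might infer that Method, Preference and interaction compete for primacy. Sections II and III put Method first, and that stands. On weighting, Section V sizes differences "between the 2 groups of each design variable" with equal cells, which suggests an equally weighted effect. However, Preference is observed, not allocated ("each patient will be asked to state which method of cesarean delivery she would prefer"), so the cells need not come out equal. With the interaction in the model, the averaging should be written down.

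**The questionnaire may settle it.** It could contain an overall item or a scoring key. For that reason the point is limited to the supplied text. Even so, a scoring key would not say which score is tested, in which model and at what alpha. That belongs in Section VIII.

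**The any-item rule is hypothetical.** This is true, and the 43% is a ceiling. Yet at an assumed correlation of 0.9 the error is still 13%, more than twice the nominal 5%.

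**Conclusion.** The point holds as a gap in the definition of the primary outcome and in type I error control. The supplied text does not say which satisfaction result decides the primary objective, and the alpha in Section V does not describe the analysis listed in Section VIII. The size (37% to 13% in either direction, 19% to 7% in the favorable one) depends on the any-item rule and on assumed common correlations of 0.3 to 0.9. That the supplied text gives neither a deciding variable nor a multiplicity rule depends on no assumption.

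The figure of 508 is not in question. Nor do the documents show that the satisfaction analysis was chosen after seeing results by Method: Section VII reports interim analyses and a survey revision but does not say whether satisfaction by Method was examined. Because this concerns the primary objective, it should be settled before further outcome data are analysed.

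**What to change.** In Section VIII:

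1. **Name one primary satisfaction variable.** Either (A) the patient's mean over the 11 items, if the questionnaire supports a single scale scored in one direction, in a linear mixed model; or (B) one designated overall-satisfaction item, if there is one, in an ordinal mixed model.
2. **Test the Method effect on it once,** two-sided at 0.05, adjusted for Preference, with the planned physician-within-hospital intercept. If the interaction is kept, state how Method is averaged over the preference groups. Fitting the primary model without the interaction is an option, not a requirement.
3. **Make the rest secondary.** Report the other items, the Preference effect and the interaction descriptively or with Holm adjustment.
4. **Keep 508 and restate the power.** Under A, use a justified SD for the composite. Under B, give a detectable odds ratio under a stated answer distribution.
5. **Date the choice** and record what satisfaction data by Method had been seen at interim analyses. This is disclosure and does not fully restore prespecification.

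The cost is SAP wording, a check of the questionnaire's content and scoring direction, and one restated power calculation. No new data are needed. Under A, a rule for partly answered questionnaires is also needed. The downside is that single-item results can no longer be claimed as primary evidence. A composite also dilutes an effect confined to a few items: 0.5 points on 3 of 11 items is 0.5 × 3/11 = 0.14 points on the mean.
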